Patients were randomly allocated to either DEEP group or non-DEEP group before the procedure. Patients were informed of the group to which they have been randomized.

H. Procedure:

The electrophysiological study and ablation was conducted under general anesthesia under supervision of an anesthesiologist. Continuous Non-invasive or intra-arterial blood pressure monitoring and digital pulse oximetry were performed. ICD therapies were inactivated.

Vascular sheaths were inserted into the right femoral vein (2 to 3), right femoral artery and/or subxiphoid area under local anesthesia (bupivacaine). A steerable quadripolar or decapolar catheter was positioned in the right ventricular apex or coronary sinus. The access was via endocardial retroaortic approach, trans-septal approach, epicardial approach or endocardial retroaortic with ad-hoc epicardial approach. Epicardial mapping and ablation was performed when preprocedural ce-

CMR showed epicardial scar, endocardial mapping did not identify subendocardial scars, unipolar LV mapping suggested the presence of epicardial scar, ECG of clinical or induced VT suggests epicardial origin (Berruezo *et al.*, 2004) (Vallès, Bazan and Marchlinski, 2010). The right ventricle (RV) was mapped when right ventricular origin of VT was suspected e.g. in arrhythmogenic right ventricular cardiomyopathy (ARVC). Surface electrocardiograms (ECGs) and bipolar intracardiac electrograms were continuously monitored.

I. Mapping and Ablation Strategy:

All patients underwent bipolar voltage mapping during sinus rhythm. Mapping was performed by either an irrigated tip ablation catheter (ThermoCool SF™ catheter; Biosense Webster, Diamond Bar, CA, USA), (ThermoCool ST™ catheter; Biosense Webster, Diamond Bar, CA, USA), (FlexAbility™; Abbott, St. Paul, MN, USA), (TactiCath™; Abbott, St. Paul, MN, USA) or a multi-electrode mapping catheter (Pentaray™, Biosense Webster, Diamond Bar, CA, USA). Late potentials (LPs) (defined as sharp high frequency or fractionated potentials at or after the terminal portion of QRS (Arenal *et al.*, 2003)) were pinpointed and tagged.

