The study population was followed up for a mean duration of 12 months for the occurrence of the study endpoints. The primary endpoint was VT recurrence rates. Secondary endpoints were all-cause mortality and cardiovascular mortality. For patients with implanted defibrillators, follow up was done by interrogation of device recordings, while when defibrillators were not implanted, follow up was by history taking for the occurrence of symptoms or need for emergency department admission attributed to recurrence of VT.

K. Statistical analysis:

Continuous variables with normal distribution are presented as mean \pm standard deviation and range whilst those with non-normal distribution are reported as median and interquartile range (IQR). Continuous variables were compared by Student's t-test, while categorical variables were compared by chi-square tests, or Fisher's exact tests as appropriate. Statistical analysis were performed using SPSS 25 for Windows (SPSS Inc, Chicago, Illinois, USA).

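### The primary endpoint has no time horizon, follow-up is given only as a mean, and the analysis section has no time-to-event method and no rule for censoring or death

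*Combined protocol and SAP*

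**What the plan says.** The Follow up section (J) states: "The primary endpoint was VT recurrence rates". It does not say by when, or whether a rate means a proportion, a time to first event or episodes per unit of patient-time. Duration appears once: "The study population was followed up for a mean duration of 12 months for the occurrence of the study endpoints". The documents give no minimum, maximum, fixed visit or closing date. The Patients section puts recruitment between October 2021 and January 2023, so entry was staggered.

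The same section adds: "Secondary endpoints were all-cause mortality and cardiovascular mortality". The plan therefore expects deaths, and a death prevents any later recurrence. For patients with a defibrillator, "follow up was done by interrogation of device recordings"; "when defibrillators were not implanted, follow up was by history taking". Neither route has a schedule.

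The Statistical analysis section (K) compares continuous variables by t-test, and "categorical variables were compared by chi-square tests, or Fisher's exact tests as appropriate". It names the software and stops there. No Kaplan-Meier, log-rank, Cox, person-time or competing-risk method appears in the documents, nor any rule for loss, censoring or death before VT.

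**The concern.** By inference, the primary comparison is the proportion of patients in each arm with any recorded recurrence, whatever their length of observation. A mean of 12 months does not show that any given patient was observed for 12 months. Such a proportion belongs to no defined risk period, and it treats a recurrence in week 2 and one in month 11 alike. A patient who dies without VT could be counted as free of recurrence, left out, or counted as a failure.

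Two competent analysts could report different primary results from the same data. The crude comparison may also waste power by ignoring event times. Bias between arms is a separate matter. It would need follow-up, loss or mortality to differ by arm, and the documents show no such difference.

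**Working it through.** The plan states no sample size, event rate, effect size or power, so it has no figure to reproduce. What follows illustrates the size of the problem. Only the 12-month mean and the recruitment dates come from the documents.

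**Assumptions.** The 12-month VT risk is 30% with constant hazard λ = −ln(0.7)/12 = 0.02972 per month. Arms have 30 or 50 patients. Two spreads with mean 12 months are used: uniform 4 to 20, as about 16 months of even accrual and one common close-out would give, and uniform 10 to 14, as visits near 12 months would give.

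**1. Undefined risk period.** The risk by month t is 1 − exp(−λt).

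- Uniform 4 to 20: 11.2% at 4 months and 44.8% at 20 months.
- Uniform 10 to 14: 25.7% at 10 months and 34.0% at 14 months.

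The expected crude proportion is 1 − [exp(−λa) − exp(−λb)]/[λ(b − a)]. It is 29.3% for 4 to 20 and 30.0% for 10 to 14, close to the true 30%. Read as an incidence rate, the same hazard is 1200λ = 35.7 per 100 patient-years.

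**2. No death rule.** Let m be the assumed 12-month mortality and d = −ln(1 − m)/12, independent of VT. Over 12 months:

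- VT or death: A = 1 − 0.7(1 − m)
- VT first: V = A × λ/(λ + d)
- Death without VT: D = A − V

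For m = 10%: d = 0.00878, A = 0.370, V = 0.370 × 0.7720 = 0.2856, D = 0.0844. Excluding such deaths gives 0.2856/(1 − 0.0844) = 0.312.

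| Mortality | Counted as no recurrence (V) | Excluded, V/(1 − D) | Counted as failure (A) |
|---|---|---|---|
| 5% | 29.3% | 30.6% | 33.5% |
| 10% | 28.6% | 31.2% | 37.0% |
| 20% | 27.1% | 32.6% | 44.0% |

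This moves the level in both arms and is not bias. If mortality were 5% in one arm and 20% in the other with equal VT hazards, 12-month cumulative incidence would differ by 2.2 points (29.3% v 27.1%) and the crude proportion over 4 to 20 months by 2.4 (28.6% v 26.2%). Only the cause-specific hazard ratio would be unaffected.

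**3. Type I error.** With equal hazards and the same follow-up distribution in both arms, simulated chi-square type I error at nominal two-sided 5% is 4.8 to 5.2%.

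**4. Power.** Simulated (40,000 runs per scenario, constant hazard), uncorrected chi-square to log-rank, in percent:

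| Spread, n per arm | 20% v 40% | 30% v 60% | 50% v 75% |
|---|---|---|---|
| 4–20, 30 | 36.8 to 38.7 | 60.4 to 64.8 | 44.6 to 53.5 |
| 4–20, 50 | 56.0 to 58.6 | 83.4 to 86.2 | 66.6 to 75.5 |
| 10–14, 30 | 39.3 to 40.2 | 66.0 to 66.9 | 51.5 to 56.1 |
| 10–14, 50 | 59.2 to 59.7 | 87.5 to 87.5 | 74.2 to 77.6 |

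The gain is 2 to 9 points for 4 to 20 and 0 to 5 for 10 to 14. An intermediate spread of 8 to 16 gives 1 to 6. With a front-loaded hazard (Weibull shape 0.5) the gains are about 1 to 5 for 4 to 20 and 0 to 5 for 10 to 14.

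These gains need proportional hazards. With a 30% base risk and a hazard ratio of 3 confined to the first 6 months, log-rank gains 7 to 8 points. If the ratio applies only after month 6, log-rank gains nothing over 4 to 20 and loses 5 to 8 points over 10 to 14.

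**The case against.** The strongest reply is that the harm is small. Allocation was random ("Patients were randomly allocated to either DEEP group or non-DEEP group before the procedure"), so follow-up should be similar by arm and the chi-square test keeps its size. The expected crude proportion is within a point of the 12-month risk. The 11% to 45% range describes individual patients under an assumed close-out, not error in the reported figure, and it shrinks to 26% to 34% if visits cluster near 12 months. All of this stands, and it is why no bias is claimed.

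Counting death without VT as failure is also the least plausible reading, because mortality is a separate endpoint and nothing suggests a composite. That is fair. The choice between no recurrence and exclusion still moves the result by 1.3, 2.6 and 5.5 points at 5%, 10% and 20% mortality.

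Finally, chi-square or Fisher would suit a fixed 12-month endpoint with complete follow-up, so the lack of a survival method is not a fault in itself, and the power gain is conditional. Both points hold. The power argument is secondary, and the fixed-horizon remedy is accepted below. But the plan sets no such horizon. A valid test of a quantity with no stated period or death rule still leaves that quantity undefined.

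**Conclusion.** The concern holds and should be fixed. The documents give no time point for the primary endpoint, state follow-up only as a mean, and contain no time-to-event method or rule for censoring, loss or death. That much rests on the text alone.

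The certain cost is a primary result with no defined risk period and no defined handling of death, whatever the spread of follow-up. The numerical illustrations rest on an assumed 30% risk, constant hazards, 5 to 20% mortality and an assumed spread. The possible power loss additionally assumes arm sizes and effect sizes, and its sign can reverse if the arms differ only late. Bias and type I error inflation are not part of the finding.

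**What to change.** In the Statistical analysis section (K):

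- Define the primary endpoint as time from procedure to first VT recurrence, censored at last device check or contact, or at death without VT.
- Make log-rank the single primary test, with a Cox hazard ratio and 95% CI.
- Report 12-month cumulative incidence per arm with death without VT as a competing event. State that this risk, unlike the cause-specific hazard ratio, is affected by mortality differences.
- Use Kaplan-Meier and log-rank for all-cause mortality.
- State the assumption of non-informative censoring, and report follow-up duration and losses by arm.
- Keep chi-square and Fisher tests for baseline and procedural variables.

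An LVEF-adjusted Cox model and a competing-risk method for cardiovascular death are optional.

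**Acceptable alternative.** Use a fixed 12-month yes/no endpoint with a written rule for deaths and losses. It keeps the planned tests but needs every patient followed to 12 months, which is January 2024 for the last enrolled.

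**Cost.** Low, with no extra patients. The time-to-event route needs an event date and a last-contact date for each patient. Device interrogation should supply dates where a defibrillator is implanted (an assumption); dates from history taking will be imprecise. The documents do not show whether the named software ("Statistical analysis were performed using SPSS 25 for Windows") gives competing-risk estimates.

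Log-rank does not repair outcome-related loss. If 20% of recurrences in one arm go unrecorded because the patient is lost, simulated type I error at 30% base risk is 7 to 9% for log-rank and 8 to 10% for chi-square. At 50% base risk it is about 9 to 11% and 12 to 18%.

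The text is in the past tense. If outcomes have been seen, label the new analysis post hoc and show the chi-square result beside it.

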Patients allocated to the DEEP group were subjected to further analysis of their LPs by RV extrastimulus pacing. This constituted an S1 drive train at 600 ms or 500 ms (according to the sinus rhythm cycle length) followed by a single S2 extrastimulus at 20 ms longer than the ventricular effective refractory period. Thereafter, the time interval from the surface ventricular far-field signal to the local bipolar LP electrogram was measured both during the RV drive train and with S2 extrastimulus. If the difference between the 2 measured values was > 10 ms, the analyzed LP was annotated as a DEEP. The same applied for multicomponent signals where DEEP was annotated if there was a more than 10 ms splitting of components in response to S2 (Figure 1) (Porta-Sánchez *et al.*, 2018). The percentage of points with LPs and DEEPs was calculated in relation to the total number of mapped points.

Figure (1): Intracardiac electrogram demonstrating DEEP

Figure (1): Intracardiac electrogram of a patient with arrhythmogenic right ventricular cardiomyopathy during right ventricular S1-S2 pacing. The late component of the paced QRS on the distal pole of ablation catheter shows significant delay with extrastimulation denoting a DEEP

Ablation was performed by ThermoCool SF™ catheter (Biosense Webster), ThermoCool ST™ catheter (Biosense Webster), FlexAbility™ (Abbott) or TactiCath™ (Abbott). Concerning the DEEP group, ablation was initially restricted to points with DEEPs, while in the non-DEEP group, ablation aimed at elimination of all LPs. Acute success was defined as VT non-inducibility, including both clinical and non-clinical tachycardias. If VT was still inducible after ablation, activation and entrainment mapping were performed for hemodynamically-tolerated tachycardias, aiming at identification of the critical components of the re-entrant circuit -according to previously defined criteria (Brunckhorst *et al.*, 2004)(Stevenson *et al.*, 1997),

followed by ablation at such locations. If the VT was untolerated, pacemapping was performed aiming at a $> 96\%$ match (Bogun *et al.*, 2006).

J. Follow up:

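### Does naming only Student's t-test for continuous variables, when skewed ones are reported as medians, need correcting?

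*Combined protocol and SAP*

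**What the plan says.** Section K of the combined protocol and SAP first separates continuous variables by shape. Roughly normal ones get a mean, standard deviation and range, while "those with non-normal distribution are reported as median and interquartile range (IQR". The next sentence turns to testing and drops the separation: "Continuous variables were compared by Student's t-test", "while categorical variables were compared by chi-square tests, or Fisher's exact tests as appropriate". The closing qualifier belongs to the choice between chi-square and Fisher. No rank-based test, transformation or rule for judging normality appears anywhere in the document.

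Section J (Follow up) lists what the trial is meant to decide: "The primary endpoint was VT recurrence rates. Secondary endpoints were all-cause mortality and cardiovascular mortality". Section I (Mapping and Ablation Strategy) adds a binary procedural result: "Acute success was defined as VT non-inducibility".

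The one derived continuous measure is also in Section I: "The percentage of points with LPs and DEEPs was calculated in relation to the total number of mapped points".

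**The concern.** A plan that recognises skewed variables for presentation but not for testing looks internally inconsistent. Taken literally, a row with two medians would carry a p-value about means. If the t-test is instead read as applying only to the normal variables, the skewed ones have no planned test.

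Three consequences would matter if they were real:

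- a false-positive rate above the nominal level in modest, skewed samples;
- loss of power compared with a rank test;
- a reader seeing similar medians beside a small p-value and drawing the wrong inference.

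The variables most open to this are the percentage of mapped points with late potentials, the number of mapped points, and earlier VT episodes or shocks if recorded as counts. That any of these is skewed is an assumption. The documents do not say so.

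**Working it through.** **Step 1: what the sentence governs.**

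| Quantity | Where | Type | Under the t-test sentence? |
|---|---|---|---|
| VT recurrence (primary) | Section J | event | No |
| All-cause and cardiovascular mortality | Section J | event | No |
| Acute success | Section I | binary | No |
| DEEP percentage | Section I | continuous, DEEP arm only | No between-arm test |
| Late-potential percentage, number of mapped points | Section I | continuous or count, both arms | Yes |
| Age, ejection fraction, LV dimensions, laboratory values, prior episodes if counted | Sections A, D, E | baseline | Yes |

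The DEEP row follows from "Patients allocated to the DEEP group were subjected to further analysis of their LPs by RV extrastimulus pacing": the other arm has no value to compare. Late potentials exist in both arms because "All patients underwent bipolar voltage mapping during sinus rhythm", with tagging in that same mapping step.

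**Step 2: what a test of those rows can show.** History and baseline measurements precede randomisation, so any arm difference is due to chance. There is no effect to detect and power has no practical meaning; only the false-positive rate matters. Late-potential percentage and number of mapped points come after allocation, but before the DEEP analysis and before ablation differ between arms. The documents name no continuous variable measured after the strategies diverge.

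**Step 3: false positives.** The documents give no sample size, distribution or effect size, so there is no figure of theirs to reproduce. Everything from here is assumed: two-sided 0.05, and 10,000 or 20,000 simulated trials per setting. With both arms drawn from the same skewed distribution, the t-test rejected in 2.6% to 5.0% of trials at 15, 30 and 50 per arm (lognormal, log-SD 0.5 to 1.5). Over a wider set of shapes at 20, 30 and 50 per arm it rejected in 2.8% to 5.1%. Where it departs from 5%, it is mainly on the conservative side.

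**Step 4: power.** Difference = Mann-Whitney power minus t-test power, at an assumed 30 per arm.

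| Assumed difference between arms | t-test | Mann-Whitney | Difference (points) |
|---|---|---|---|
| Lognormal, 2-fold, log-SD 0.5 | 99.9% | 99.9% | 0 |
| Lognormal, 2-fold, log-SD 1.0 | 57% | 73% | +16 |
| Lognormal, 2-fold, log-SD 1.5 | 20% | 39% | +19 |
| Beta percentage, 20 vs 30%, skewness 0.9 | 76% | 76% | 0 |
| Beta percentage, 5 vs 10%, precision 8 | 61% | 79% | +18 |
| Beta percentage, 5 vs 10%, precision 4 | 40% | 70% | +30 |
| Normal, 0.7 SD shift | 76% | 73% | −3 |
| Exponential, mean doubled | 72% | 61% | −11 |
| Overdispersed count, mean 4 vs 8 | 65% | 55% | −10 |

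At 50 per arm, the lognormal doubling with log-SD 1.5 gives 31% against 61%, again +30. The sign therefore depends on the shape. Counts of earlier episodes, one of the natural candidates, resemble the row where the t-test does better.

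**Step 5: medians beside a p-value for means.** Take two lognormals, both with median 1, with log-SD 0.5 and 1.0. The mean is exp(log-SD²/2): exp(0.125) = 1.13 and exp(0.5) = 1.65. The t-test gives p<0.05 in 10%, 18% and 35% of trials at 20, 30 and 50 per arm; Mann-Whitney gives about 6%. The t-test is correctly detecting unequal means, so these are not false positives. The example also favours Mann-Whitney by construction. Both variables are symmetric about zero on the log scale, so the probability that a value from one arm exceeds one from the other is exactly 0.5, which is the value a rank test looks for departures from. In general Mann-Whitney is not a test of medians, so substituting it would not guarantee that the p-value matches the printed summary.

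**The case for a change.** The strongest case for a change is that the plan itself provides for non-normal variables and then gives them either the wrong test or none. A sentence or two would settle it, SPSS 25 offers both tests, and stating in advance how a variable is classed would remove discretion. Under marked skew the power given up can be large, about 30 points in two of the settings above. In addition, VT recurrence rates is not defined further. If it were analysed as a per-patient count of episodes, the t-test sentence would reach the primary endpoint.

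The textual point stands in full: the wording is incomplete, and this is not an artefact of how the text was extracted. The power figures also stand as arithmetic, but they describe comparisons in which no treatment effect is in question, and they reverse for other plausible shapes. The discretion argument is weaker than it sounds. The obvious classing rule, a normality pre-test such as Shapiro-Wilk, has little power in small arms and flags trivial departures in large ones, so it would replace one debatable choice with another. The episode-count reading of the primary endpoint is possible, but nothing in the text supports it. A proportion or a time to first recurrence is the natural reading, and neither is a continuous variable compared by a t-test.

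**Conclusion.** No change is needed. Section K leaves a gap between how skewed variables are summarised and how they are tested, but the gap is confined to descriptive and mapping rows. No endpoint, acute-success result or trial conclusion depends on it.

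In the settings run, the t-test did not inflate false positives (2.6% to 5.1%). Replacing it with Mann-Whitney moved power by anything from about −11 to about +30 points at an assumed 30 per arm, depending on a distribution the documents do not give. That is a trade-off without a clear winner, in rows where power matters little. An analyst faced with a clearly skewed row can apply a rank test and label it, and nothing else in the trial would move.

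This rests on three assumptions: VT recurrence is analysed as an event and not as a per-patient episode count; the continuous comparisons are those the documents identify, none of them measured after the strategies diverge; and the simulated shapes and arm sizes, none of which come from the documents, are a fair illustration.

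### VT recurrence is compared only by tests of difference, with no effect estimate or confidence interval, so a non-significant result could not tell similar recurrence from too little information

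*Combined protocol and SAP*

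**What the plan says.** Section J (Follow up) defines the endpoint: "The primary endpoint was VT recurrence rates". Follow-up averages 12 months.

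Section K (Statistical analysis) covers descriptive summaries, Student's t-test for continuous variables, and the software. It says that "categorical variables were compared by chi-square tests", with Fisher's exact test where suitable. It plans no effect estimate and no confidence interval. Neither section K nor any other part of the document gives a hypothesis, a margin, a significance level, a sample size or a rule for reading a non-significant result.

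Section I (Mapping and Ablation Strategy) sets the randomised contrast. In the DEEP arm "ablation was initially restricted to points with DEEPs", while "in the non-DEEP group, ablation aimed at elimination of all LPs". A DEEP is a late potential (LP) that meets one further criterion: "If the difference between the 2 measured values was > 10 ms, the analyzed LP was annotated as a DEEP". The same section provides for additional treatment: "If VT was still inducible after ablation, activation and entrainment mapping were performed for hemodynamically-tolerated tachycardias", with ablation at the sites found and pacemapping for tachycardias that are not tolerated. That step is not limited to one arm.

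**The concern.** The experimental arm begins with a narrower set of targets than the control arm. In such a comparison a finding of no significant difference in recurrence is easily taken as good news for the narrower strategy. A test of no difference cannot support that. A p-value above 0.05 arises when the arms are truly alike, and also when the trial is too small to show that they differ.

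What separates the two cases is the interval around the estimated difference, and the plan does not call for one. A reader of the planned output would not learn how much excess recurrence in the DEEP arm the data still allow. This bears on the primary endpoint.

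**Working it through.** The plan states no sample size, power, significance level or expected recurrence, so it has no figure to reproduce. Everything below rests on assumed inputs: two-sided 5% level, equal arms, and 30% recurrence in the control arm.

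**1. Are the first-line targets nested?** Control targets: all LPs. DEEP targets: LPs whose interval changes by more than 10 ms at S2. The second set lies within the first. One detail is not explicit: the rule is extended to multicomponent signals without repeating that these must be LPs. Hence essentially, rather than strictly, a subset.

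**2. Does the p-value carry the information needed?** Take 30% recurrence observed in both arms, once with 20 and once with 100 patients per arm. The counts are 6/20 v 6/20 and 30/100 v 30/100. The observed difference is zero in each case, so the chi-square p-value is 1 both times. The 95% CI half-width for the risk difference is

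1.96 × √(2 × 0.30 × 0.70 / n)

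| n per arm | half-width |
|---|---|
| 20 | 0.284 (28 points) |
| 30 | 0.232 (23 points) |
| 50 | 0.180 (18 points) |
| 100 | 0.127 (13 points) |

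The same p-value is thus compatible with an excess of up to 28 points in one trial and 13 in the other.

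**3. A less tidy example.** Suppose 9/30 recurrences in control and 12/30 with DEEP.

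- Difference = 0.40 − 0.30 = 0.10.
- Standard error = √(0.30 × 0.70/30 + 0.40 × 0.60/30) = 0.1225.
- 95% CI = 0.10 ± 1.96 × 0.1225 = −0.14 to +0.34.
- Chi-square p = 0.42; Fisher p = 0.59.

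The planned output would be the p-value. The interval shows that a 34-point excess is not excluded.

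**4. How often would a real excess be missed?** For each pair of true risks, I summed the binomial probabilities of every pair of counts for which the uncorrected chi-square test is not significant, that is |z| < 1.96 with z = (a − b)/n ÷ √(2q(1 − q)/n) and q = (a + b)/(2n).

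| True recurrence, control v DEEP | n = 20 | n = 30 | n = 50 | n = 100 |
|---|---|---|---|---|
| 30% v 40% | 0.896 | 0.877 | 0.820 | 0.684 |
| 30% v 45% | 0.836 | 0.781 | 0.656 | 0.406 |
| 30% v 50% | 0.755 | 0.649 | 0.454 | 0.168 |
| 30% v 60% | 0.537 | 0.337 | 0.124 | 0.008 |

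The chance of missing the excess varies from very high to negligible, depending on a size and an effect that the document does not give.

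**The case against.** The strongest reply is that the plan makes no claim that the test would have to support. It states no equivalence or non-inferiority aim and sets no rule for p > 0.05. Superiority of DEEP fits the text equally well. That is right, and it rules out three stronger readings that a reader might infer.

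- **That the DEEP arm receives less ablation overall.** The restriction is only the starting strategy. If VT stays inducible, further mapping and ablation follow in either arm, so total ablation need not be smaller. The plan also names no endpoint for the extent of ablation, so it sets up no comparison of that kind.
- **That a non-significant result is the likely outcome even if DEEP is clearly worse.** The document gives a recruitment window (October 2021 to January 2023) but no expected number of patients. With 100 per arm, 30% v 45% would be detected 59% of the time (1 − 0.406). With 50 per arm, 30% v 60% would be detected 88% of the time (1 − 0.124).
- **That following the plan leads to a wrong conclusion.** The plan yields a p-value and prescribes no conclusion. An error would need a misreading that the plan does not endorse.

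It can also be said that the missing hypothesis and sample size are the deeper defects. They are related, but supplying them would not by itself put an interval around the primary result. What remains after all this is the core point. Whatever the aim was, a p-value alone cannot show what a null result allows.

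**Conclusion.** The point holds in a limited form. Section K plans only tests of difference for VT recurrence, with no effect estimate or interval, in a trial whose experimental arm starts from essentially a subset of the control arm's targets. A non-significant result reported that way could not distinguish similar recurrence from imprecision.

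This conclusion rests on the text and needs no assumed figure. Its practical size does. At an assumed 30% v 45%, the excess is missed 84%, 78%, 66% and 41% of the time at 20, 30, 50 and 100 per arm. Other assumptions move these figures a long way in both directions. The change should be made: it concerns the primary endpoint and costs very little.

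**What to change.** In section K:

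1. Make the primary result the DEEP minus non-DEEP difference in VT recurrence risk with a two-sided 95% CI, and give the chi-square or Fisher p-value beside it.
2. State that p > 0.05 will be reported as inconclusive, not as equivalence or non-inferiority, and that the conclusion will name the largest excess recurrence that the interval does not exclude.

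No margin has to be chosen for this. A claim of non-inferiority would be a different matter, since its margin would have to be fixed and justified before outcome data were seen.

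A hazard ratio with its CI is an alternative only if event and censoring times are available; it cannot be obtained from the 2 × 2 table. Follow-up is described only by its mean, so if the risk difference is used, the plan should say over what period recurrence is counted.

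Cost: two sentences in the plan and one interval from the table already needed for the test. The downside is that the conclusion may read less favourably.
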